## 1 Protocol Synopsis

**PROTOCOL TITLE:** Phase II Study of Ofatumumab in Combination with High Dose Methylprednisolone followed by Ofatumumab and Lenalidomide consolidative therapy for the treatment of untreated CLL/SLL: The HiLOG trial.

DATE PROTOCOL FINAL:	June 20, 2011
INDICATION:	Untreated CLL/SLL
STUDY PHASE:	Phase II

**BACKGROUND AND RATIONALE:** Chronic lymphocytic leukemia (CLL), the most common leukemia in the Western countries, is characterized by a progressive accumulation of functionally incompetent monoclonal B lymphocytes. CLL is considered to be identical (same disease at different stages) to the mature B-cell small lymphocytic lymphoma (SLL). CLL is typically considered a disease of the elderly, with a median age at diagnosis of 72 years. The disease remains non curable by current treatment options with the possible exception of allogeneic hematopoietic stem cell transplantation. In addition, the vast majority of patients diagnosed with CLL are older than 65 and many times have significant co-morbidities. This makes it difficult for most patients with CLL to tolerate traditional chemotherapy regimens due to the associated toxicities. A non-chemotherapeutic regimen that provides high efficacy with less toxicity than conventional regimens would be desirable in this population. We are proposing a combination regimen consisting of high dose methylprednisolone combined with ofatumumab, followed by consolidative therapy with lenalidomide in combination with ofatumumab. (See Table 1 for dosing and details of treatment regimen). The rationale for exploring this combination regimen is based on the following previously published trials:

Results of a phase II study combining Rituximab, an anti CD20 monoclonal antibody, with high dose methylprednisolone as a salvage regimen for the treatment of patients with fludarabine refractory CLL showed an overall response rate (ORR) of 93% with a complete remission rate (CR) of 36%. The regimen was well tolerated, and serious adverse events were rare. All patients were able to complete the scheduled treatment without delays or dosage reductions. Another recent paper from the same group

showed similar efficacy in the front line setting using a reduced dose of steroids. They showed an ORR of 96% with a CR rate of 32%. 

Ofatumumab (Arzerra®) is a human monoclonal antibody that targets a unique small-loop epitope on CD20 and elicits potent *in vitro* complement-dependent cytotoxicity, even in malignant B cells with low levels of CD20 expression. Ofatumumab is currently approved by the FDA for fludarabine and alemtuzumab refractory CLL. It is also under development by Novartis for the treatment of untreated, relapsed or refractory B-cell follicular lymphoma, for the treatment of untreated CLL, for the treatment of active rheumatoid arthritis, and other autoimmune diseases.

Ofatumumab has been studied in patients with fludarabine and alemtuzumab refractory CLL (FA-ref) or refractory to fludarabine with bulky (>5cm) lymphadenopathy (BF-ref).  Ofatumumab was given weekly x 8 doses followed by monthly infusions x 4. Results of a planned interim analysis included 138 treated patients with FA-ref (n = 59) and BF-ref (n = 79) CLL. The overall response rates (primary end point) were 58% [corrected] and 47% in the FA-ref and BF-ref groups, respectively. Complete resolution of constitutional symptoms and improved performance status occurred in 57% and 48% of patients, respectively. Median progression-free survival and overall survival times were 5.7 and 13.7 months in the FA-ref group, respectively, and 5.9 and 15.4 months in the BF-ref group, respectively. The most common adverse events during treatment were infusion reactions and infections, which were primarily, grade 1 or 2 events. Hematologic events during treatment included anemia and neutropenia. These encouraging results in patients with refractory CLL warrant further investigation of ofatumumab in combination with other agents, and as maintenance for the treatment of patients with CLL.

Lenalidomide is a novel immunomodulating anticancer agent that was designed to enhance immunologic and anticancer properties while potentially decreasing neurotoxic and teratogenic adverse effects of the parent compound thalidomide. Its exact antitumor mechanism remains elusive. However, its antitumor activity seems to be mediated through its ability to modulate production of various key survival cytokines such as TNF-

$\alpha$ , IL-6, IL-8 and VEGF in the tumor microenvironment. Lenalidomide has also been shown to affect other components of the tumor microenvironment, including the immune cellular compartment. Preclinical studies demonstrated that lenalidomide enhances NK-cell mediated and monocyte-mediated tumor cell ADCC for a variety of rituximab treated NHL cell lines in vitro. A Phase II trial of single agent lenalidomide in patients with relapsed or refractory CLL revealed an ORR of 47% with a CR rate of 9%. Another phase II trial of single agent lenalidomide for the treatment of relapsed or refractory CLL revealed an ORR of 32% with 7% CR, 25% stable disease. The most common toxicity was myelosuppression, and the median daily dose of lenalidomide tolerated was 10 mg. More recently two combination trials of lenalidomide and rituximab have been reported in abstract form from our center and the MDACC. Both of these studies evaluated patients with relapsed disease and showed an overall response rate of 60%.

Our hypothesis is that ofatumumab will produce higher rates of CR in this setting. The consolidation with lenalidomide is based on the fact that this drug has activity in CLL but is not immunosuppressive. In addition, there is evidence that lenalidomide can improve the immune system of patients with CLL as well as increase the rates of CR in this population. The reason for incorporating lenalidomide after debulking patients with high dose steroids and ofatumumab is based on the experience with lenalidomide as a single agent in the relapsed and front line setting. In this setting tumor lysis syndrome and tumor flare were observed. We believe that this sequence of drugs will carry less toxicity and will be better tolerated.

Table 1. HiLOG Clinical Study Dosing Schema

Week	Study Day	HDMP	Ofatumumab	Lenalidomide
1	Cycle 1 Day 1	1000 mg/m 	300 mg	
2	Cycle 1 Day 8	1000 mg/m 	2000 mg	
3	Cycle 1 Day 15	1000 mg/m 	2000 mg	
4	Cycle 1 Day 22	1000 mg/m 	2000 mg	
5	Cycle 2 Day 1	1000 mg/m 	2000 mg	
6	Cycle 2 Day 8			
7	Cycle 2 Day 15	1000 mg/m 	2000 mg	
8	Cycle 2 Day 22			
9	Cycle 3 Day 1	1000 mg/m 	2000 mg	
10	Cycle 3 Day 8			

Amendment 5 Dated 03/02/2016

11	Cycle 3 Day 15	1000 mg/m 	2000 mg		
12	Cycle 3 Day 22				
13	Cycle 4 Day 1			5-10 mg pd Days 1-28 as per Cr Cl	
17	Cycle 5 Day 1			5-10 mg pd Days 1-28 as per Cr Cl	
21	Cycle 6 Day 1		2000 mg	5-10 mg pd Days 1-28 as per Cr Cl	
25	Cycle 7 Day 1			5-10 mg pd Days 1-28 as per Cr Cl	
29	Cycle 8 Day 1		2000 mg	5-10 mg pd Days 1-28 as per Cr Cl	
33	Cycle 9 Day 1			5-10 mg pd Days 1-28 as per Cr Cl	
37	Cycle 10 Day 1		2000 mg	5-10 mg pd Days 1-28 as per Cr Cl	
41	Cycle 11 Day 1			5-10 mg pd Days 1-28 as per Cr Cl	
45	Cycle 12 Day 1		2000 mg	5-10 mg pd Days 1-28 as per Cr Cl	

#### **STUDY OBJECTIVES:**

##### **Primary:**

1. To estimate the response rate for the combination of ofatumumab with high dose methylprednisolone followed by consolidative therapy with lenalidomide and ofatumumab for patients with previously untreated CLL/SLL with indication criteria to initiate treatment (See Appendix E: Criteria for Treatment).

##### **Secondary:**

To collect preliminary efficacy data on:

1. Progression/relapse free survival.
2. Overall survival.

#### **STUDY DESIGN:**

This is a phase II, single institution, and non-randomized study of patients with untreated CLL/SLL, utilizing a two-stage trial design. The primary endpoint for this trial is the combined complete and partial response rate (at 3 months, after the end of cycle 3) to the protocol therapy. We anticipate this trial will have a CR+PR response rate of at least 80%.

A two-stage design is employed for this trial. The null/unacceptable CR+PR response rate is  $\leq 60\%$  while the anticipated true response rate to the protocol treatment is at least 80% for each disease cohort. At the first stage, 26 patients will be accrued to the trial. If 15 or fewer of these patients respond, then the trial will be terminated early and the response rate to the protocol treatment will be deemed unacceptable ( $\leq 60\%$ ). Otherwise, if more than 15 patients respond during the first stage, an additional 19 patients will be enrolled to this trial during stage 2 for a total of 45 patients. If 32 or fewer of these 45 patients respond to the protocol treatment at the end of stage 2, no further investigation of the protocol treatment is considered warranted. On the other hand, if more than 32 patients out of the 45 enrolled patients respond, the protocol treatment will be considered promising. If the true response rate is  $\leq 60\%$ , the probability of ending the trial at stage 1 is 0.48. If, however, the true response rate is at least 80%, then the probability of ending the trial at stage 1 is only 0.01. This two-stage design has an overall alpha level of 0.045 and a power of 0.90.

For the purpose of interim analysis at the end of stage 1, the objective response will be measured by the end of 3 months (or end of cycle 3) from the start of the protocol treatment prior to the initiation of the combination of ofatumumab with lenalidomide. The accrual will not be suspended while waiting for the results of the interim analysis unless the observed objective response rate among those patients whose objective response data are available is below 55%.

HiLOG Dosing Schema																										
300 mg	2000 mg doses						2000-mg doses																			
D1	D8	D15	D22	D1	D15	D1	D15	Q 2months																		
Cycle 1			Cycle 2-3			Cycle 4-12																				
▲	▲	▲	▲	▲	▲	▲	▲	Lenalidomide 5-10mg* D1-28 C4-12																		
▲ = HDMP 1000mg/m 																										
↓ = Ofatumumab																										
*10mg for CrCl>60ml/min 5mg for CrCl 30-60ml/min																										
<hr/>																										
STUDY ENDPOINTS																										
Primary:																										
• Objective response (CR+PR) rate																										
Secondary:																										
• Progression/relapse free survival.																										
• Overall survival.																										
STUDY DURATION: 2 years				TOTAL SAMPLE SIZE: up to 45																						
DOSING REGIMEN(S): Refer to dosing schema table for dosing of each drug				DRUG SUPPLIES: For study participants Novartis will provide ofatumumab, and Celgene Corporation will provide lenalidomide at no charge through the REMS® program.																						

## 2 Schedule of Study Assessments \*

Procedure	All visits/assessments may be scheduled $\pm$ 3 business days										
	Screening  <math>\leq</math> 28 days from Baseline (First day drug administration)	Cycle 1	Cycles 2 - 3	Cycle 4 				Cycles 5-12	Lenalidomide Maintenance Therapy	Discontinuation From Protocol Therapy 	Follow- Up Phase
	Days 1, 8, 15, and 22	Days 1, and 15	Day 1	Day 3 or 4 at investigator discretion	Day 8	Day 15	Day 22	Day 1 and 15			
Study drug administration **		X	X	X					X	X	
Record prior medications, treatments	X										
Record prior anti-cancer therapies	X										
Physical examination, vital signs, weight	X	X 	X 	X 					X 		
ECOG performance status	X	X 	X 	X 					X 		
ECG	X										
Assess lymphadenopathy, spleen / liver 		X 	X 	X 		X 	X 		X 		
Peripheral blood for , ZAP 70, $\beta$ -2 microglobulin, and IgHV mutational status 	X										
Research samples 	X			X							
Baseline lesion assessment	X			X							
Bone marrow 	X			X					X	X	X 
CT of the neck, chest, abdomen & pelvis 	X			X					X		X 
Hematology 	X	X	X	X 		X 	X 	X 	X 	X 	
Serum chemistry 	X	X	X	X 	X 	X 	X 	X 	X 	X 	
Hepatitis B and C serology, HBV DNA PCR 	X 										
Pregnancy testing 	X			X		X	X	X	X		
Register patient into REMS® program	X										

Prescribe lenalidomide via REMS 				X				X			
Record adverse events 		X	X	X				X	X 		
Record concomitant therapies/procedures		X	X	X				X			
Obtain Follow-Up anti-cancer treatments											X
Obtain Follow-Up survival information											X

\* An unscheduled visit can occur at any time during the study. Source must be maintained for these unscheduled visits. The date for the visit and any data generated must be recorded on the appropriate CRF. Source documents for these unscheduled visits must also be maintained.

\*\* See Table 1 for detailed study drug administration schedule.

 Physical examination of lymphadenopathy, the spleen and liver will be performed on Days 1 and 15 of Cycle 1 to access for tumor flare reaction, and on Day 1 of subsequent cycles to assess response.

 Peripheral blood for ZAP 70 IgVH mutational status, beta-2 microglobulin analyses will be done only at screening. If ZAP 70, IgVH and beta-2 microglobulin was performed within 6 months of screening date, it is not necessary to repeat at screening. Research samples for storage will be drawn during screening, day 1 of cycle 4, day 1 of Maintenance Therapy or discontinuation from protocol therapy if earlier than the end of cycle 12.

 Bone marrow studies will be performed for all subjects at baseline, at the end of cycle 3 (day 21-28 prior to cycle 4), after completion of cycle 12 and every 6 months afterwards during lenalidomide maintenance therapy for two years. Bone marrow studies at any other time point will be performed at the physician's discretion.

 CT of the neck, chest, abdomen & pelvis will be performed at screening, for response assessment at the end of cycle 3 (day 21-28 prior to cycle 4), after the end of cycle 12 (7-10 days after discontinuation of lenalidomide) and every 6 months afterwards during lenalidomide maintenance therapy for two years. After any other time point, CT scans will be performed at the physician's discretion.

 Hematology – CBC with differential WBC and platelet counts. Hematology profiles are required weekly during Cycle 4 (which corresponds to Cycle 1 of lenalidomide-containing therapy), and during any cycle in which the dose of lenalidomide is escalated or re-escalated. For subjects who are on a stable lenalidomide dose (without dose escalation or interruption of the planned dosing schedule) for  $\geq 1$  cycle of treatment, hematology profiles are required on Days 1 and 15 of the cycle.

 Chemistry includes sodium, potassium, chloride, CO2, calcium, magnesium, phosphorus, BUN, creatinine, glucose, albumin, total protein, alkaline phosphatase, total bilirubin, AST/SGOT, ALT/SGPT, LDH, and uric acid. At a minimum, for tumor lysis syndrome (TLS) monitoring purposes, subjects will have chemistry assessments weekly during at least the first 2 cycles of lenalidomide-containing treatment. Chemistry assessments on Day 3 or 4 of Cycle 1 of lenalidomide-containing treatment are at the investigator's discretion. In addition, because the risk for TLS may be elevated when lenalidomide is re-started after treatment interruptions or when the lenalidomide dose is escalated, in any cycle in which the lenalidomide dose is escalated or re-escalated or treatment is interrupted for more than 1 week, subjects may need to have weekly chemistry assessments performed for at least 4 consecutive weeks as well as an additional chemistry assessment on day 3 or 4 during the first week of escalating, re-escalating or re-initiating lenalidomide therapy. If TLS occurs, subjects will have additional chemistry assessments weekly for at least 4 consecutive weeks as well as on Day 3 or Day 4 following re-initiation of lenalidomide. For subjects who do not experience any abnormalities in serum chemistry assessments for 2 consecutive cycles while on a stable lenalidomide dose (without dose escalation or interruption of the planned dosing schedule) throughout these 2 cycles, the timing of chemistry assessments may be reduced to Day 1 and Day 15 in subsequent cycles. See section 5.6.1.1 for TLS prophylaxis instructions. To include Thyroid Stimulating Hormone (TSH) at Screening, at treatment discontinuation, and whenever clinically indicated. T3 and T4 levels may be assessed as clinically indicated.

 Hepatitis B Virus DNA by PCR will be tested at screening. If it is positive then it will be tested every 2 weeks during cycle 1, every 4 weeks during cycles 2 ad 3, and then every 2 to 3 months thereafter.

---

 Pregnancy test for females of childbearing potential. A female of childbearing potential (FCBP) is a sexually mature female who: 1) has not undergone a hysterectomy or bilateral oophorectomy; or 2) has not been naturally postmenopausal for at least 24 consecutive months (i.e., has had menses at any time in the preceding 24 consecutive months). Pregnancy tests must occur within 10 – 14 days and again within 24 hours prior to prescribing lenalidomide for Cycle 1 (prescriptions must be filled within 7 days). FCBP with regular or no menstruation must have a pregnancy test weekly for the first 28 days and then every 28 days while on lenalidomide therapy (including breaks in therapy); at discontinuation of lenalidomide and at Day 28 post the last dose of lenalidomide. Females with irregular menstruation must have a pregnancy test weekly for the first 28 days and then every 14 days while on lenalidomide therapy (including breaks in therapy), at discontinuation of lenalidomide and at Day 14 and Day 28 post the last dose of lenalidomide (see Appendix: Risks of Fetal Exposure, Pregnancy Testing Guidelines and Acceptable Birth Control Methods).

 Adverse event data entry will be captured on day 1 of each cycle. An additional safety assessment will be done 28 days (+/- 2 days) following the last dose of protocol therapy.

 If physical examination, vital signs, weight and ECOG performance status were done within 7 days of Day 1, they do not need to be repeated on Day 1. During cycle 1 the physical examination will be done on day 1 and day 15. On subsequent cycles it will be done on day 1 only.

 Lenalidomide must be prescribed through and in compliance with the REMS® program of Celgene Corporation. Prescriptions must be filled within 7 days. Consideration should be given to prescribing lenalidomide 5 to 7 days in advance of Day 1 of each cycle to allow time for required patient and prescriber surveys, and drug shipment to patient. Any unused Revlimid® (lenalidomide) should be returned to the patient for disposition in accordance with the REMS® program.

 Any required screening tests that have been performed as standard of care prior to consent and are within 28 days of starting study treatment may be used for screening and do not need to be repeated. A bone marrow biopsy performed within 6 weeks of starting study treatment does not need to be repeated during screening.

 Cycle 4 may begin up to 14 days after cycle 3 bone marrow biopsy to allow for results of response assessments to be available.

 CBC and CMP only every 4 weeks. See Section 5.8. Any grade 3 or 4 cytopenia will be recorded as an adverse event during Maintenance Therapy. No other adverse events will be recorded during Maintenance Therapy

 Upon discontinuation of study therapy, any diagnostic testing will be at the discretion of the physician.

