### **3.2.2 Ofatumumab Adverse Events**

During clinical trials of ofatumumab in FL, CLL and RA subjects, adverse events occurring during the infusions of trial drug have been reported. The following reactions should be regarded as expected infusion-related adverse reactions in connection with the use of ofatumumab probably as a consequence of B cell depletion and cytokine release: pruritus, dyspnea, bronchospasm, throat irritation, cough, pharyngolaryngeal pain, flushing, hyperhidrosis, nausea and vomiting, abdominal pain, hypotension, rash/urticaria, influenza-like-illness, fatigue, fever, chills, headache, dizziness, myalgia and arthralgia.

The incidence of infusion-related symptoms was highest during the first infusion and decreased substantially with subsequent infusions. Implementation of pre-medication before infusions has reduced the number as well as the severity of infusion related adverse events. One serious case of cytokine release complicated with laryngeal edema and one case of anaphylactoid-like reaction have been observed; both events were fully reversible after cessation of the infusion and proper treatment. It should be noted that none of these subjects received premedication with prednisolone.

During the ongoing study in subjects with CLL refractory to alemtuzumab and fludarabine, infusion related adverse events have been reported in approximately 30% of subjects. Only 2-3 % were serious adverse events. All subjects received pre-medication with prednisolone, acetaminophen and antihistamine. In the completed CLL trial 402 in patients with relapsed or refractory CLL, 15% of the subjects had serious infections. In the ongoing CLL 406 trial in subjects refractory to both alemtuzumab and fludarabine an increased frequency of serious infections (25-30%) have been reported.

---

Subjects who are HBsAg negative, anti-HBc positive and HBV DNA negative may be included in the study but must undergo HBV DNA monitoring. Consult with a physician experienced in care & management of subjects with hepatitis B to manage/treat subjects who are anti-HBc positive. Initiate anti-viral therapy if required. If a subject's HBV DNA becomes positive during the study, notify the NOVARTIS medical monitor. For subjects who have not completed planned ofatumumab therapy, discuss with the medical monitor the risks and benefits of continuing or discontinuing ofatumumab before appropriate treatment decisions are made for that individual subject.

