### **5.3.2 Exclusion criteria**

1. Any serious medical condition, laboratory abnormality, or psychiatric illness that would prevent the subject from signing the informed consent form.
2. Pregnant or breast feeding females. (Lactating females must agree not to breast feed while taking lenalidomide).
3. Any condition, including the presence of laboratory abnormalities, which places the subject at unacceptable risk if he/she were to participate in the study or confounds the ability to interpret data from the study.
4. Evidence of laboratory TLS by Cairo-Bishop Definition of Tumor Lysis Syndrome (see Appendix H). Subjects may be enrolled upon correction of electrolyte abnormalities.
5. Use of any other experimental drug or therapy within 28 days of baseline.
6. Known hypersensitivity to thalidomide.
7. The development of erythema nodosum if characterized by a desquamating rash while taking thalidomide or similar drugs.
8. Any prior use of lenalidomide.
9. Concurrent use of other anti-cancer agents or treatments.
10. Known seropositive for or active viral infection with human immunodeficiency virus (HIV)
11. Positive serology for hepatitis B (HB) defined as a positive test for HBsAg. In addition, if negative for HBsAg but HBcAb positive and HBsAb negative, a HB DNA test will be performed and if positive the subject will be excluded. Note: If HBcAb positive and HBsAb positive, which is indicative of a past infection, the subject can be included. Patients who are seropositive because of hepatitis B virus vaccine are eligible. Consult with a physician experienced in care &

management of subjects with hepatitis B to manage/treat subjects who are anti-HBc positive

12. Positive serology for hepatitis C (HC) defined as a positive test for HCAb, in which case reflexively perform a HC RIBA immunoblot assay on the same sample to confirm the result
13. Subjects who have current active hepatic or biliary disease (with exception of patients with Gilbert's syndrome, asymptomatic gallstones, liver metastases or stable chronic liver disease per investigator assessment) are ineligible.
14. Chronic or current infectious disease requiring systemic antibiotics, antifungal, or antiviral treatment such as, but not limited to, chronic renal infection, chronic chest infection with bronchiectasis, tuberculosis and active Hepatitis C.
15. History of significant cerebrovascular disease in the past 6 months or ongoing event with active symptoms or sequelae

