#### **5.4 Visit schedule and assessments**

Screening Assessments and all on study scheduled visits and assessments are outlined in Section 2: Table of Study Assessments.

Research samples for storage will be drawn during screening, day 1 of cycle 4, day 1 of Maintenance Therapy (or at time of discontinuation therapy if earlier than cycle 12). At each timepoint the following tubes will be obtained: three 10 ml green tops and one 10 ml

Amendment 5 Dated 03/02/2016

---

plain red top tube. The samples will be stored in the Moffitt Cancer Center laboratory of [name] for examining sample phenotypics and analysis of functionality of T-cell sub-populations. At treatment discontinuation, subjects will undergo off study evaluations per the Schedule of Assessments, Section 2. Study subjects who have completed the 12 cycles of treatment protocol, have not progressed while on therapy, and do not continue on lenalidomide maintenance therapy (MT) will be followed every 6 months for survival until disease progression, study closure, withdrawal of consent, or death. Subjects who progress while on MT and discontinue treatment will do the end of treatment testing. If the bone marrow biopsy and CT scans have been performed in the past 28 days to determine progression of disease, it is not necessary to repeat these tests.

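### Repeat HBV DNA testing is triggered only by a positive screening DNA, so the anti-HBc-positive, DNA-negative patients who must be monitored have no scheduled test

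*Combined protocol and SAP*

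**What the plan says.** Three parts of the protocol bear on this.

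- **The duty.** Section 3.2.2 states: "Subjects who are HBsAg negative, anti-HBc positive and HBV DNA negative may be included in the study but must undergo HBV DNA monitoring". It gives no interval. It continues: "If a subject's HBV DNA becomes positive during the study, notify the NOVARTIS medical monitor". If infusions remain, the instruction is: "For subjects who have not completed planned ofatumumab therapy, discuss with the medical monitor the risks and benefits of continuing or discontinuing ofatumumab". The same paragraph calls for consultation with a hepatitis B-experienced physician and for antiviral treatment where needed.
- **The schedule.** Section 5.4 makes Section 2 the operative list: "Screening Assessments and all on study scheduled visits and assessments are outlined in Section 2: Table of Study Assessments". The Section 2 row "Hepatitis B and C serology, HBV DNA PCR" has one mark, under screening, tied to footnote 7. That footnote has the DNA PCR done at screening and then says: "If it is positive then it will be tested every 2 weeks during cycle 1". Under the same condition, testing goes on every 4 weeks in cycles 2 and 3 and every 2 to 3 months after that.
- **Eligibility.** Exclusion 11 (Section 5.3.2) bars HBsAg-positive patients, and bars HBcAb-positive, HBsAb-negative patients whose DNA is positive. It admits others: "If HBcAb positive and HBsAb positive, which is indicative of a past infection, the subject can be included". It repeats the consultation duty, which concerns "management of subjects with hepatitis B to manage/treat subjects who are anti-HBc positive".

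**The concern.** The trigger in footnote 7 and the duty in Section 3.2.2 point at different patients. The footnote times repeat tests for patients who are DNA positive at screening, most of whom exclusion 11 keeps out. Section 3.2.2 requires monitoring of patients who are DNA negative at screening, whom exclusion 11 lets in. Staff working from Section 2, as Section 5.4 directs, would run no repeat test on the second group and would still comply with the table.

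What is at stake is patient safety. The Section 3.2.2 action rule depends on seeing DNA change from negative to positive, and only a repeated test can show that. Patients receive ofatumumab throughout cycles 1 to 12, the first eight infusions together with methylprednisolone 1000 mg/m². An unseen conversion would mean that the medical monitor is not notified and that continuing or stopping ofatumumab is not discussed.

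**Working it through.** The plan states no figure to reproduce. The check is a comparison of every hepatitis B provision, followed by simple counts.

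**Step 1. Who enters, and who is tested again**

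| Screening profile | Exclusion 11 | Repeat DNA under footnote 7 | Monitoring duty in 3.2.2 |
|---|---|---|---|
| HBsAg+ | Barred | Not applicable | Not applicable |
| HBsAg−, HBcAb+, HBsAb−, DNA+ | Barred | Not applicable | Not applicable |
| HBsAg−, HBcAb+, HBsAb−, DNA− | Admitted | None | Yes |
| HBsAg−, HBcAb+, HBsAb+, DNA− | Admitted | None | Yes |
| HBsAg−, HBcAb+, HBsAb+, DNA+ | Not barred by 11 (3, 13, 14 or 17 might apply) | Full series | Not named |

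The two rows with a monitoring duty are the two admitted rows with no repeat test. Among HBcAb-positive patients, the only route into footnote 7's series is the last row.

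**Step 2. Does another provision supply the test?**

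- Liver stopping rules (5.5.2.1.1): these act only once ALT has risen.
- Liver Chemistry Follow-up Assessments: for hepatitis B these list HBsAg and core IgM, not HBV DNA.
- Infection prophylaxis (5.6.1.5): this names Pneumocystis, herpes virus and fungal cover, not hepatitis B.
- Footnote 15: after discontinuation, diagnostic testing is at the physician's discretion.
- Unscheduled visits: allowed, with no HBV DNA trigger.

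Scheduled post-screening HBV DNA tests for the Section 3.2.2 group: **0**.

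**Step 3. Exposure over which this holds (Table 1)**

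- Ofatumumab infusions: 4 (cycle 1) + 2 (cycle 2) + 2 (cycle 3) + 4 (cycles 6, 8, 10, 12) = 12.
- First to last infusion: (45 − 1) × 7 = 308 days.

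**Step 4. Liver chemistry in the same patients (schedule and footnote 6; discretionary day 3 or 4 draws not counted)**

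- Minimum: 4 (cycle 1) + 2 × 2 (cycles 2–3) + 2 × 4 (cycles 4–5, weekly) + 7 × 2 (cycles 6–12, days 1 and 15) = 30 draws.
- If weekly testing continues through cycle 12: 4 + 2 × 2 + 9 × 4 = 44 draws.

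This measures the partial safeguard, not the gap.

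**Step 5. Tests needed if footnote 7's timetable were applied to this group**

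- Cycle 1, every 2 weeks: 28 / 14 = 2.
- Cycles 2–3, every 4 weeks: 56 / 28 = 2.
- Cycles 4–12: 9 × 28 = 252 days, and 252 / 30.4375 = 8.28 months. Counting whole intervals, every 3 months gives 2 and every 2 months gives 4.
- Total through cycle 12: 2 + 2 + 2 = 6 to 2 + 2 + 4 = 8.
- Each year of maintenance: 12 / 3 = 4 to 12 / 2 = 6.
- With 2 years of maintenance: 6 + 8 = 14 to 8 + 12 = 20.

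**The case against.** The strongest reply is that monitoring is not missing, only its interval. Section 3.2.2 is mandatory text, footnote 7 does not cancel it, and both can be followed at once because they cover different groups. Leaving the interval to the hepatitis B consultant is defensible. The safeguards are real: consultation, antiviral therapy if required, at least 30 liver chemistry draws and liver stopping rules. The footnote may also be a drafting slip. It hangs on a row that includes serology, so a reader might take the trigger to be positive serology, and the near-empty DNA-positive branch suggests anti-HBc was intended.

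Much of this stands. The duty binds, the safeguards reduce the risk, and the timetable in footnote 7 was not written for DNA-negative patients, so it should not be imposed rigidly. But the protocol does not hand the interval to the consultant. It asks for consultation on management and treatment and sets no DNA test. The sentence before the trigger names only the DNA PCR, so the serology reading is the weaker one, and if it was intended the footnote still needs correcting. Frequent ALT testing is not the DNA monitoring that Section 3.2.2 requires.

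**Conclusion.** The concern holds. A mandatory safety test has no scheduled timepoint for the group it was written for, and the conditional timetable that does exist is aimed mainly at patients the eligibility criteria exclude. This should be fixed, though it is not a threat to the trial's inference: the primary endpoint, alpha, power and two-stage rule do not depend on it.

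The conclusion rests on reading the trigger as referring to the DNA PCR, which is what the sentence says. The practical size depends on how many of the up to 45 patients are anti-HBc positive and DNA negative. The documents do not give that number, and it may be zero.

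A minor, separate point is that Section 3.2.2 words inclusion in terms of DNA-negative patients, whereas exclusion 11 sets no DNA condition for those positive for both HBcAb and HBsAb. Section 3.2.2 does not say that DNA-positive patients are barred, so this is only a matter of aligning the wording.

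**What to change.** Amend footnote 7 so that the repeat series applies if screening HBV DNA is positive **or** if the patient is anti-HBc positive, HBsAg negative and DNA negative. Keep the existing intervals as the default and allow the hepatitis B consultant to set and document a different interval for DNA-negative patients. State whether testing continues into lenalidomide maintenance. Mark the conditional timepoints in the table row and cross-reference Section 3.2.2.

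The cost is one footnote sentence and one table row by amendment, using an assay already in the protocol. At the default intervals this is about 6 to 8 tests per affected patient through cycle 12, plus 4 to 6 a year if testing continues in maintenance. Maintenance may run until progression, so that total has no fixed ceiling. If no such patient enrols, no tests are added.

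Requiring a negative HBV DNA for all HBcAb-positive patients in exclusion 11 is optional. It would align the wording, but it changes eligibility and would leave the DNA-positive trigger with almost no one at screening. The scheduling fix does not need it. Sample size, alpha, power and the two-stage rule stay as they are.
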